13.1.5.1. Association of Biochemistry with Clinical Outcomes and Clinical Benefit

The association between the effect of OCA on ALP and bilirubin and the clinical benefit of OCA will be evaluated by estimating the proportion of net treatment effect on the primary composite endpoint that is explained by each biochemical marker. For each biochemical endpoint, this proportion will be estimated by applying the partial likelihood function to two Cox models that use the same failure time variable, as described in [Lin 1997](#). This analysis will be based on the ITT population.

Based on the association between biochemical changes and clinical outcomes described above, clinical benefit of OCA for key subpopulations of interest will be evaluated. This analysis will be further described in the SAP.

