Hematology	Hemoglobin, hematocrit, white blood count with differential, neutrophils, lymphocytes, monocytes, eosinophils, basophils, platelets, red blood cell count (including MCV, MCH, MCHC)
Coagulation	Prothrombin time (PT), partial thromboplastin time (PTT), international normalized ratio (INR)
Urinalysis	pH, specific gravity, total protein, glucose, ketones, bilirubin, blood, microscopic exam, urobilinogen, albumin, creatine, leucocytes, nitrates, albumin/creatinine ratio (if positive)
Biomarkers of Hepatic Fibrosis and/or Inflammation	IgM, C-reactive protein (CRP), TNF- α , FGF-19, CK-18, ELF, and others as determined during course of study
Genetics	DNA including single-nucleotide polymorphisms (SNPs) that may be involved in PBC; RNA
Blood Sample for Future Analysis	PBC autoantibodies and other cytokines and interleukins TBD
Other	OCA (parent and conjugates [glyco and tauro], OCA-glucuronide) and C4

The Investigator should manage subjects with clinically significant lipoprotein abnormalities using local standard of care procedures as appropriate after assessing the individual subject's total cardiovascular risk profile.

Urine-based β -hCG pregnancy tests will be performed in female subjects of childbearing potential per protocol specified visits. If a urine pregnancy test is positive, a serum pregnancy test must be performed to confirm the result. If positive, the Sponsor must be notified and the subject will be followed, as outlined in [Section 12.1.9](#) through pregnancy outcome.

MELD scores, Child-Pugh score, and MRS will be calculated at screening, and at quarterly (MELD and Child-Pugh scores) or semi-annual (MRS) visits based on serum chemistry and coagulation.

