13.1.3. Primary Efficacy Analysis

The primary efficacy endpoint will be the time to first occurrence of one of the following post-randomization:

- Death (all-cause)
- Liver transplant

- MELD score ≥ 15
- Hospitalization (as defined by a stay of 24 hours or greater) for new onset or recurrence of:
 - Variceal bleed
 - Hepatic encephalopathy (as defined by a West Haven score of ≥ 2)
 - Spontaneous bacterial peritonitis (confirmed by diagnostic paracentesis)
- Uncontrolled ascites (diuretic resistant ascites requiring therapeutic paracentesis at a frequency of at least twice in a month).
- Hepatocellular carcinoma confirmed by 2 complimentary imaging modalities unless confirmed by biopsy

The primary efficacy analysis will compare randomized OCA to randomized placebo with respect to the primary efficacy endpoint using the ITT population. Only adjudicated events will be included in analyses. The 2 treatment groups will be compared using the log rank test stratified by the randomization stratification factor. Kaplan-Meier (KM) estimates of the distribution of the time-to-event will be tabulated and graphed by treatment group. The tabulation will include the KM estimate of the medians and corresponding 95% confidence intervals (CIs), if the medians can be estimated. The number and percent of subjects censored and with events will be presented. The hazard ratio and 95% CI will be determined based on a Cox regression model stratified by randomization strata to estimate the magnitude of the effect.

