
Section 13.1.5.1 Association of Biochemistry with Clinical Outcomes and Clinical Benefit
	
Insertion
	
13.1.5.1 Association of Biochemistry with Clinical Outcomes and Clinical Benefit
 
The association between the effect of OCA on ALP and bilirubin and the clinical benefit of OCA will be evaluated by estimating the proportion of net treatment effect on the primary composite endpoint that is explained by each biochemical marker. For each biochemical endpoint, this proportion will be estimated by applying the partial likelihood function to two Cox models that use the same failure time variable, as described in Lin 1997. This analysis will be based on the ITT population.
 
Based on the association between biochemical changes and clinical outcomes described above, clinical benefit of OCA for key subpopulations of interest will be evaluated.
	
This analysis will provide additional insight into the connection between surrogate endpoints and clinical outcome events allowing for evaluation of benefit in subpopulations for which the study is not powered.

		
This analysis will be further described in the SAP.
	

13.1.8 Supportive Analysis
	
Insertion
	
Although the study is designed as a placebo-controlled study, the DMC may recommend changes to study conduct based on the pre-specified interim analyses (see Section 13.1.12), including the potential use of a revised primary efficacy analysis. This analysis would compare all subjects in the OCA population, to all control subjects (randomized placebo and historical controls) on time to liver transplant or death (all-cause) (see Section 13.1.2.1), using similar statistical methodology as specified above.
 
Notably, the planned primary analysis would not be revised without prior agreement with regulatory authorities.
	
As a placebo-controlled study, the alternative primary analysis section has been removed.
 
Upon review of blinded data, the DMC may recommend changes to study conduct. However, such recommendations will not be implemented unless the Sponsor has received agreement from regulatory authorities.

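### The proportion of OCA's effect explained by bilirubin is estimated on a composite that counts MELD ≥15, a score computed partly from bilirubin, so the bilirubin result is partly circular

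*Protocol*

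**What the plan says.** Section 13.1.5.1 names the markers: "The association between the effect of OCA on ALP and bilirubin and the clinical benefit of OCA will be evaluated". It names the outcome: "estimating the proportion of net treatment effect on the primary composite endpoint that is explained by each biochemical marker". It names the method: "applying the partial likelihood function to two Cox models that use the same failure time variable". It then carries the association forward, so that "clinical benefit of OCA for key subpopulations of interest will be evaluated". Appendix G gives the reason for adding the section, which includes "allowing for evaluation of benefit in subpopulations for which the study is not powered".

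Section 13.1.3 lists "MELD score ≥ 15" among the components of the primary composite. Section 12.2.7 says that MELD is calculated at quarterly "visits based on serum chemistry and coagulation". Table 10 in that section puts total bilirubin and creatinine in the chemistry panel and INR in the coagulation panel.

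The text shown plans no proportion-explained analysis on an outcome without MELD. Section 13.1.5.1 leaves the subpopulation work to be described further in the SAP, but it fixes the outcome itself.

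This wording is from Version 3.1. The Version 4 synopsis keeps MELD in the composite and removes hepatocellular carcinoma. The Version 4 table of contents keeps the heading of Section 13.1.5.1, but the text of that section is not shown.

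**The concern.** A proportion-explained analysis asks how far the treatment effect on an outcome shrinks once the marker is adjusted for. The answer is informative when the marker and the outcome are separate measurements. Here, a fall in bilirubin lowers MELD arithmetically, whether or not a death, transplant or decompensation is prevented. Adjusting for bilirubin then removes treatment effect that bilirubin itself put into the outcome.

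The result has a use beyond description. It supports statements about benefit in subpopulations that, by the sponsor's own account in Appendix G, the study is not powered to examine directly. A proportion that is too high for bilirubin would make a biochemical change in those groups look like stronger evidence of clinical benefit than it is.

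**Working it through.** **The plan's own figures.** The protocol gives no figure for this analysis. Its design figures reproduce and are not in question. At HR 0.60, two-sided 5% and 80% power, the Freedman formula gives 126 events and the Schoenfeld formula 121. Allowing for the two interim looks (factor 1.020) gives 128 and 123, against the stated 127. With exponential survival, 4 years of accrual and 6 of follow-up, the pooled event probability is 0.331. Then 127/0.331 = 384, and 384/0.9 = 427 with the 10% dropout of Version 4, against 428.

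**How near bilirubin can bring a subject to the threshold.** The protocol does not print the MELD formula. I assume the standard weights with creatinine at 1 mg/dL, so that bilirubin at MELD 15 = exp((15 − 6.43 − 11.2 ln INR)/3.78):

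- INR 1.0: exp(8.57/3.78) = 9.7 mg/dL
- INR 1.3: exp(5.63/3.78) = 4.4 mg/dL
- INR 1.5: exp(4.03/3.78) = 2.9 mg/dL

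At normal INR a large rise is needed. At raised INR a moderate bilirubin value is enough.

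**Effect on the proportion explained (illustrative).** The proportion is 1 − (adjusted log HR / unadjusted log HR). The simulation used 40,000 subjects, 40 quarterly visits and grouped-time Cox models, with and without MELD ≥15 in the endpoint. OCA lowers log bilirubin by 0.25 in the base case. The protocol does not say how the marker enters the model, so both a time-dependent covariate and a one-year landmark are shown. The documents give neither the share of MELD-first events nor the marker effect, so both are assumptions.

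| Scenario | MELD-first share | Time-dependent: without → with MELD | Landmark: without → with MELD |
|---|---|---|---|
| Partial mediation (base case) | 18% | 0.50 → 0.80 | 0.40 → 0.55 |
| Bilirubin not causal for clinical events | 29% | 0.18 → 0.75 | 0.04 → 0.40 |
| Smaller bilirubin effect (0.10) | 20% | 0.19 → 0.38 | 0.18 → 0.31 |
| Few MELD-first events | 6% | 0.45 → 0.56 | 0.35 → 0.41 |
| Full mediation | 14% | 1.48 → 1.71 | 0.92 → 0.94 |
| OCA has no effect on bilirubin | 24% | −0.10 → −0.14 | −0.03 → −0.03 |
| OCA also lowers ln INR by 0.06 | 16% | 0.50 → 0.60 | 0.38 → 0.44 |
| OCA also lowers ln INR by 0.15 | 13% | 0.48 → 0.45 | 0.36 → 0.34 |
| OCA also lowers ln INR by 0.25 | 12% | 0.43 → 0.35 | 0.33 → 0.29 |

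Two reruns of the base case with other seeds gave 0.46 → 0.74 and 0.49 → 0.80 (time-dependent).

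**Precision of an estimate without MELD.** The design z-value is |ln 0.60| × √(127/4) = 0.511 × 5.63 = 2.9. If 6% to 29% of events are MELD-first and are simply dropped, 127 × 0.94 = 119 to 127 × 0.71 = 90 events remain, and z is 2.8 to 2.4. At an assumed share of 35% to 54%, 83 to 58 remain, and z is 2.3 to 1.95. These counts are lower bounds, because some of those subjects will later have another component event.

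**The case against.** The strongest case on the other side has four parts.

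First, the section is an additional secondary analysis outside the gatekeeping sequence, and Section 13.1.10 treats tests of additional endpoints as descriptive. The trial's confirmatory claim rests on the log rank test of the composite. This stands: type I error, power and the primary conclusion are untouched.

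Second, a treatment effect confined to MELD would be visible. Transplant or all-cause death is a key secondary endpoint (Section 13.1.4), and the other components and liver-related death are analysed separately (Section 13.1.5). This limits the harm, but it does not correct the proportion explained or the subpopulation statement built on it.

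Third, a reader might infer that the bilirubin proportion must be inflated, or that it could exceed 100% with no clinical event prevented. The documents do not support either as a finding. The table shows no inflation when bilirubin does not change, almost none under full mediation with a landmark, and reversal with a large separate INR effect. A result above 100% with no clinical event prevented does arise in a scenario where clinical events are independent of both treatment and bilirubin and 35% to 54% of first events are MELD. Those shares have no source in the protocol, and the scenario runs against the protocol's own premise in Section 5.5.1 that bilirubin gauges clinical risk. A reader might also extend the point to ALP because one sentence covers both markers, but ALP is not an input to MELD.

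Fourth, the section text is Version 3.1, and whether Version 4 changed it cannot be seen. That has to be checked before the comment is sent.

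**Conclusion.** The point holds for bilirubin. The protocol itself names the composite as the outcome and bilirubin as a marker, so a SAP that follows it inherits the overlap. The bilirubin proportion is partly circular and is expected to be too high if OCA lowers bilirubin, clinical events are not fully mediated by it, and OCA has no large separate effect on INR.

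The size is not computable from the documents. Under the assumptions shown, with OCA lowering bilirubin and having no separate effect on INR, the shift ran from almost nothing (0.92 → 0.94) to large (0.18 → 0.75). It depended mainly on how far bilirubin mediates the clinical events, on the share of MELD-first events and on how the marker is modelled. That bilirubin is an input to MELD rests on the definition of the score, and is consistent with Section 12.2.7 and Table 10.

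What is at stake is the surrogacy statement for bilirubin and the subpopulation benefit drawn from it, and nothing in the primary analysis.

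**What to change.** In Section 13.1.5.1, after confirming that the Version 4 text is unchanged on this point:

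- For bilirubin, also estimate the proportion explained on the primary composite without the MELD component. This keeps more events than the alternatives.
- Give the same estimate for transplant or all-cause death as support.
- Report the full-composite result alongside, labelled as sharing bilirubin with its outcome.
- State that subpopulation benefit inferred through bilirubin will not rest on the full-composite estimate alone.
- Report the confidence interval of every proportion explained.

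The ALP analysis can stay as it is.

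The cost is some wording and two further pairs of Cox models: one on a key secondary endpoint already derived, the other on a composite built from components already adjudicated. The real price is precision. The estimate is a ratio whose denominator is the treatment effect, and its Fieller interval becomes unbounded once that effect's z-value falls below 1.96. With many MELD-first events the z-value comes close to that limit. For this reason the MELD-free result should stand beside the full-composite one and should not be made the sole basis for the subpopulation inference.

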13.1.6. Exploratory Efficacy Analyses

13.1.6.1. Responder Analyses

The percentage of subjects with a decrease in ALP of $\geq 15\%$ and $\geq 40\%$ from Baseline will be summarized by treatment group. In addition, the percentage of subjects with $ALP \leq ULN$ will be summarized by treatment group.

The percentage of subjects that meet the criteria of a responder based on each of the definitions below will be summarized by treatment group. The response classification at baseline will also be included in the summary:

- $ALP \leq 3 \times ULN$ and $AST \leq 2 \times ULN$ and total bilirubin $\leq ULN$ ([Corpechot 2008](#))
- $ALP \leq 1.5 \times ULN$ and $AST \leq 1.5 \times ULN$ and total bilirubin $\leq ULN$ ([Corpechot 2011](#))
- $ALP \leq 1.67 \times ULN$ and total bilirubin $\leq ULN$ ([Momah 2012](#))
- Normal bilirubin (values $\leq ULN$) and normal albumin (values \geq lower limit of normal) ([Kuiper 2009](#))
- $ALP \leq 1.76 \times ULN$ ([Kumagi 2010](#))

Responder analyses will compare treatment groups using a Cochran–Mantel–Haenszel test stratified by the randomization stratification factor. Missing values will be considered as a non-responder.

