To assess the effect of OCA compared to historical controls on liver-related clinical outcomes.
 To characterize the pharmacokinetics of OCA and its conjugates in a subset of subjects.
 To assess health outcomes and pharmacoconomics including cost-effectiveness, resource utilization, and quality of life measures in subjects treated with OCA compared to placebo.
 To assess the safety and tolerability in subjects treated with OCA compared to placebo.

Methodology:

This Phase 4, double-blind, randomized, placebo-controlled, multicenter study will evaluate the effect of OCA on clinical outcomes in subjects with PBC. Subjects will be screened twice during a 1 to 8-week Screening period prior to entering the study to allow for the collection of repeat serum chemistry samples (at least 2 weeks apart) to confirm pretreatment alkaline phosphatase (ALP) and total bilirubin values (refer to Section 9.7.6).

Investigational product will be taken orally, once daily for the majority of subjects; dose and frequency will be modified for subjects with cirrhosis (including subjects progressing to cirrhosis during the study) and classified as Child-Pugh B or C. The randomization will be stratified by ursodeoxycholic acid (UDCA) treatment (yes/no) and baseline bilirubin categories (> upper limit of normal [ULN]/ ≤ ULN).

Schematic Diagram:

EOS = end of study; ULN = upper limit of normal
 Initial dose titration of investigational product should occur at the Month 3 visit, or any study visit thereafter for subjects on all dosing regimens, based on tolerability and biochemical response. Subsequent dose titration(s) for subjects classified as Child-Pugh B or Child-Pugh C and following a modified dosing schedule may occur no earlier than 6 weeks after the previous dose titration.

Dosing frequency will be determined by the presence or absence of cirrhosis and, if cirrhosis is present, by Child-Pugh Score as described below:

- Non-cirrhotic subjects or subjects classified as Child-Pugh A at screening will receive 5-mg OCA or matching placebo once daily for 3 months. Subjects should titrate to a maximum dose of 10-mg OCA once daily (or matching placebo) at the Month 3 visit or at any study visit following the Month 3 visit based on tolerability and biochemical response of the product.

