- For those subjects that up-titrate to 10 mg, dosing may be decreased to 5 mg at any time during the study as considered clinically appropriate (eg, based on tolerability). Subjects may be titrated back to a maximum dose of 10 mg once daily based on tolerability and clinical judgment of the Investigator.
- Subjects who are cirrhotic and classified as Child-Pugh Class B or Child-Pugh Class C will initiate a modified treatment regimen with 5-mg OCA or matching placebo once weekly for at least 3 months. Subjects classified as Child-Pugh Class B should eventually titrate to a maximum dose of 5-mg OCA or matching placebo once daily, based on tolerability and biochemical response. Subjects classified as Child-Pugh Class C should titrate to a maximum dose and frequency of 10-mg OCA or matching placebo twice weekly, based on tolerability and biochemical response.

Planned Dosing Regimen by Cirrhosis and Child-Pugh Score			
	Planned Dosing Regimen		
	Standard	Modified	
	Non-Cirrhotic/ Child-Pugh A	Child-Pugh B	Child-Pugh C
Starting Dose^a (Day 0)	5 mg daily	5 mg once weekly	5 mg once weekly
Titration 1^b (≥Month 3)	10 mg daily	5 mg twice weekly	5 mg twice weekly
Titration 2^b (≥6 weeks after Titration 1)	NA	10 mg twice weekly	10 mg twice weekly
Titration 3^b (≥6 weeks after Titration 2)	NA	5 mg daily	NA

^a Starting dose based on subject's cirrhosis status and Child-Pugh Score at Screening.

^b Planned titration regimen is shown; however, the titration of dose and/or frequency is dependent on subject tolerability, biochemical response, and/or changes in cirrhosis status or Child-Pugh Score at any time during the study.

Number of Subjects (planned):
Approximately 428 subjects

Diagnosis and Main Criteria for Inclusion:
Inclusion Criteria

- Definite or probable PBC diagnosis (consistent with American Association for the Study of Liver Diseases [AASLD] and the European Association for the Study of the Liver [EASL] practice guidelines; Lindor 2009; EASL 2009), as demonstrated by the presence of ≥2 of the following 3 diagnostic factors:
 - History of elevated ALP levels for at least 6 months
 - Positive antimitochondrial antibody (AMA) titer or if AMA negative or in low titer (<1:80) PBC-specific antibodies (anti-GP210 and/or anti-SP100 and/or antibodies against the major M2 components [PDC-E2, 2-oxo-glutaric acid dehydrogenase complex])
 - Liver biopsy consistent with PBC
- A mean total bilirubin >ULN and ≤5× ULN and/or a mean ALP >3× ULN
- Age ≥18 years

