13.1.9.3. Responder Endpoints

In an efficacy analysis in which subjects are classified as either a responder or a non-responder (binary outcome) based on dichotomizing a continuous variable, any subject who does not provide an assessment at the specified time point for the defining of response will be considered to be a non-responder. That is, for the percentage of responders, the subject will be included in the denominator and will not contribute to the numerator.

For sensitivity analyses using only “observed cases,” subjects who do not provide an assessment at the specified timepoint for the defining of response will not be included. That is, for the percentage of responders, the subject will not be included in the numerator or the denominator.

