13.1.10. Multiple Comparisons/Multiplicity

The key secondary efficacy endpoints are as follows:

- Time to MELD score ≥ 15
- Time to first occurrence of liver transplant or death (all-cause)
- Change from Baseline in total bilirubin at end of study
- Change from Baseline in ALP at end of study

The hypothesis testing of key secondary analyses will compare placebo and OCA and will be conducted in a sequential closed testing gate-keeping procedure (in the order in which the key secondary endpoints are stated above), provided that the primary efficacy endpoint comparison is statistically significant in favor of OCA. If the primary comparison is not statistically significant then comparison of the secondary endpoints will be considered as descriptive and exploratory. This procedure controls the study-wise type I error.

- First (step 1) placebo and OCA will be compared with respect to the primary efficacy endpoint. If the comparison achieves statistical significance at 2-sided 0.05 level in favor of OCA group, then
- The time to MELD score ≥ 15 will be compared between placebo and OCA (step 2). If the comparison achieves statistical significance at 2-sided 0.05 level in favor of OCA group, then
- The time to liver transplant or death (all-cause) will be compared between placebo and OCA (step 3). If the comparison achieves statistical significance at 2-sided 0.05 level in favor of OCA group, then
- Change from Baseline in total bilirubin will be compared between placebo and OCA (step 4). If the comparison achieves statistical significance at 2-sided 0.05 level in favor of OCA group, then
- Change from Baseline in ALP at the end of study will be compared between placebo and OCA (step 5).

If at any step defined above the comparison is not statistically significant at the 2-sided 0.05 level then the remaining comparisons in the stated hierarchy will be considered descriptive and exploratory. The study-wise type I error will be maintained with the above closed procedure.

Additional efficacy endpoints will be analyzed; however, hypothesis tests will be applied for descriptive and exploratory purposes only.

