To assess the effect of OCA compared to historical controls on liver-related clinical outcomes.
 To characterize the pharmacokinetics (PK) of OCA and its conjugates in a subset of subjects.
 To assess health outcomes and pharmacoeconomics including cost-effectiveness, resource utilization, and quality of life measures in subjects treated with OCA compared to placebo.
 To assess the safety and tolerability in subjects treated with OCA compared to placebo.

Methodology:

This Phase 4, double-blind, randomized, placebo-controlled, multicenter study will evaluate the effect of OCA on clinical outcomes in subjects with PBC. Subjects will be screened twice during a 1- to 8-week Screening period prior to entering the study to allow for the collection of repeat serum chemistry samples (at least 2 weeks apart) to confirm pretreatment alkaline phosphatase (ALP) and total bilirubin values (refer to Section 9.7.6).

Investigational product will be taken orally, once daily for the majority of subjects; dose and frequency will be modified for subjects with cirrhosis (including subjects progressing to cirrhosis during the study) and classified as Child-Pugh B or C. The randomization will be stratified by ursodeoxycholic acid (UDCA) treatment (yes/no) and baseline bilirubin categories (> upper limit of normal [ULN]/ ≤ULN). A minimum of 30% of subjects will have elevated bilirubin (>ULN) at Screening.

Schematic Diagram Study 747-302:

EOS = end of study; ULN = upper limit of normal
 Initial dose titration of investigational product should occur at the Month 3 visit, or any study visit thereafter for subjects on all dosing regimens, based on tolerability and biochemical response (up-titration should be considered when ALP and/or total bilirubin are >ULN). Subsequent dose titration(s) for subjects classified as Child-Pugh B or Child-Pugh C and following a modified dosing schedule may occur no earlier than 6 weeks after the previous dose titration.

Dosing frequency will be determined by the presence or absence of cirrhosis and, if cirrhosis is present, by Child-Pugh Score as described below:

- Noncirrhotic subjects or subjects classified as Child-Pugh A at screening will receive 5-mg OCA or matching placebo once daily for 3 months. Subjects should titrate to a maximum dose of 10-mg OCA once daily (or matching placebo) at the Month 3 visit or at any study visit following the Month 3 visit based on tolerability and biochemical response of the product.

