 - Positive antimitochondrial antibody (AMA) titer or if AMA negative or in low titer (<1:80) PBC-specific antibodies (anti-GP210 and/or anti-SP100 and/or antibodies against the major M2 components [PDC-E2, 2-oxo-glutaric acid dehydrogenase complex])
 - Liver biopsy consistent with PBC
- A mean total bilirubin >ULN and ≤5x ULN and/or a mean ALP >3x ULN
- Age ≥18 years
- Either is not taking UDCA (no UDCA dose in the past ≥3 months) or has been taking UDCA for at least 12 months with a stable dose for ≥3 months prior to Day 0
- Contraception: Female subjects of childbearing potential must use ≥1 effective method of contraception during the study and until 30 days following the last dose of investigational product. Effective methods of contraception are considered to be those listed below:
 - Barrier method, ie, (a) condom (male or female) or (b) diaphragm, with spermicide
 - Intrauterine device (IUD)
 - Vasectomy (partner)
 - Hormonal (eg, contraceptive pill, patch, intramuscular implant or injection)
 - Abstinence, if in line with the preferred and usual lifestyle of the subject
- Must provide written informed consent and agree to comply with the study protocol

Exclusion Criteria

1. History or presence of other concomitant liver diseases including:
 - Hepatitis C virus infection
 - Active hepatitis B infection; however, subjects who have seroconverted (hepatitis B surface antigen and hepatitis B e antigen negative) may be included in this study after consultation with the Medical Monitor
 - Primary sclerosing cholangitis
 - Alcoholic liver disease
 - Definite autoimmune liver disease or overlap hepatitis
 - Nonalcoholic steatohepatitis
 - Gilbert's Syndrome
2. Presence of clinical complications of PBC or clinically significant hepatic decompensation, including:
 - History of liver transplant, current placement on a liver transplant list, or current MELD score >12. Subjects who are placed on a transplant list despite a relatively early disease stage (for example per regional guidelines) may be eligible as long as they do not meet any of the other exclusion criteria
 - Cirrhosis with complications, including history (within the past 12 months) or presence of:
 - Variceal bleed
 - Uncontrolled ascites
 - Encephalopathy
 - Spontaneous bacterial peritonitis
 - Known or suspected HCC
 - Prior transjugular intrahepatic portosystemic shunt procedure
 - Hepatorenal syndrome (type I or II) or Screening (Visit 1 or 2) serum creatinine >2 mg/dL (178 µmol/L)

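### Two of the five responder rules, and the ALP ≤ULN summary, can already be met at entry, so the planned CMH test on them mixes new response with maintenance

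*Protocol*

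**What the plan says.** Section 13.1.6.1 lists five published responder definitions:

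1. ALP ≤3×ULN, AST ≤2×ULN and bilirubin ≤ULN
2. ALP ≤1.5×ULN, AST ≤1.5×ULN and bilirubin ≤ULN
3. ALP ≤1.67×ULN and bilirubin ≤ULN
4. normal bilirubin and normal albumin
5. ALP ≤1.76×ULN

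It also summarises the percentage with ALP ≤ULN, and ALP falls of at least 15% and 40% from Baseline. None of the five rules, nor ALP ≤ULN, requires a change from Baseline. Entry status is mentioned only for display: "The response classification at baseline will also be included in the summary".

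The test is fixed: "Responder analyses will compare treatment groups using a Cochran–Mantel–Haenszel test stratified by the randomization stratification factor". The strata come from the synopsis (and Section 9.4): "The randomization will be stratified by ursodeoxycholic acid (UDCA) treatment (yes/no) and baseline bilirubin categories". A subject without an assessment is a non-responder, and under Section 13.1.9.3 "the subject will be included in the denominator and will not contribute to the numerator".

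Inclusion criterion 2 in Version 3.1 is "A mean total bilirubin >ULN and ≤5× ULN and/or a mean ALP >3× ULN", and Version 4 keeps the same limits. The Version 4 synopsis adds: "A minimum of 30% of subjects will have elevated bilirubin (>ULN) at Screening".

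**The concern.** The and/or in the entry rule lets a subject enter with one marker high and the other well inside a responder threshold. Take someone enrolled with ALP 4×ULN, bilirubin 0.6×ULN and normal albumin. If nothing changes, that subject is a responder under the bilirubin/albumin rule. Someone enrolled with bilirubin 2×ULN and ALP 1.5×ULN is, unchanged, a responder under ALP ≤1.76×ULN. A subject enrolled on bilirubin with normal ALP counts under ALP ≤ULN.

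On these measures the response rate adds two quantities: subjects who reach the threshold on study, and subjects who were there at the start and stayed. A reader cannot tell from the CMH result which of the two OCA affected. If OCA acts only on the first, the baseline responders add variance and shrink the difference.

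**Working it through.** **Step 1. Which rules can be met at entry?** An eligible subject has bilirubin >ULN (up to 5×ULN), or ALP >3×ULN, or both.

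| Measure | Needs | Possible at entry? | Bilirubin stratum |
|---|---|---|---|
| ALP ≤3×, AST ≤2×, bilirubin ≤ULN | bilirubin ≤ULN and ALP ≤3×ULN | No | none |
| ALP ≤1.5×, AST ≤1.5×, bilirubin ≤ULN | the same, tighter | No | none |
| ALP ≤1.67×, bilirubin ≤ULN | the same, tighter | No | none |
| Normal bilirubin and albumin | bilirubin ≤ULN | Yes, if enrolled on ALP | ≤ULN only |
| ALP ≤1.76× | ALP ≤1.76×ULN | Yes, if enrolled on bilirubin | >ULN only |
| ALP ≤ULN (summary) | ALP ≤ULN | Yes, if enrolled on bilirubin | >ULN only |

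The first three need bilirubin ≤ULN together with ALP ≤3×ULN or lower, which fails criterion 2. A grid over ALP 0.3–12×ULN and bilirubin 0.1–5×ULN gives the same table.

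**Step 2. Does the planned stratification separate them?** Only partly. Each affected measure has its baseline responders in one bilirubin stratum, but they share it with baseline non-responders.

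**Step 3. Size, for the bilirubin/albumin rule.** The protocol gives no rate or power for these analyses, so there is no planned figure to reproduce.

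From the documents: 428 subjects randomised 1:1, so 214 per arm. Version 4 requires at least 30% with bilirubin >ULN, so at most 70% are ≤ULN (0.70 × 428 ≈ 300).

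Assumed: 85% of the ≤ULN group have normal albumin; response in all other subjects is 30% (OCA) versus 15% (placebo); 90% of baseline responders on OCA keep their status.

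Share of baseline responders: f = 0.70 × 0.85 = 0.595. Reported rate in an arm: p = f × retention + (1 − f) × response.

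- OCA: 0.595 × 0.90 + 0.405 × 0.30 = 0.657
- Placebo, 90% retained: 0.595 × 0.90 + 0.405 × 0.15 = 0.596; difference 0.061
- Placebo, 80% retained: 0.595 × 0.80 + 0.405 × 0.15 = 0.537; difference 0.120
- Baseline non-responders only: 0.30 − 0.15 = 0.150, in about 0.405 × 214 ≈ 87 per arm

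Simulated power, two-sided 5%, CMH stratified by bilirubin category:

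| Placebo retention | Planned, all subjects | Baseline non-responders only | All subjects, baseline status added as stratum |
|---|---|---|---|
| 90% | 0.33 | 0.66 | 0.42 |
| 80% | 0.83 | 0.66 | 0.91 |

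Holding stratum sizes fixed instead of drawing them moves the planned figures only to 0.32 and 0.86.

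With equal 90% retention and a smaller share at ≤ULN, planned versus restricted power is 0.59 versus 0.81 (50% at ≤ULN) and 0.82 versus 0.90 (30%).

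**Step 4. Adding the stratum.** Across 12 combinations (30%, 50% or 70% at ≤ULN; placebo retention 75% to 90%), the CMH with baseline status as a stratum beat the planned test every time. Its type I error stayed near 5%.

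**The case against.** **Most rules are untouched.** Three of the five cannot be met at entry. A reader might infer that the reported response rates in general describe who was enrolled. For those three the entry criteria rule it out, apart from a few subjects who might cross a threshold if Baseline takes in Day 0 values as well as the screening means. This stands.

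**Maintenance may be part of the benefit.** Section 5.1 describes a disease that often progresses without treatment, and follow-up is expected to last at least about 6 years. Keeping normal bilirubin and albumin could itself be an OCA effect. A reader might infer that the all-subject test always loses power and should give way to a test in baseline non-responders. Step 3 contradicts that: a 10-point retention difference reverses the order, to 0.83 against 0.66. This stands too, and it decides the form of the fix.

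**No bias and no confirmatory role.** Randomisation balances baseline responders, so neither bias nor type I error inflation can be inferred. The section is exploratory, and Section 13.1.10 says: "Additional efficacy endpoints will be analyzed; however, hypothesis tests will be applied for descriptive and exploratory purposes only". This stands and limits the weight of the point.

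**The plan already discloses it.** Baseline classification is tabulated, and the ALP-decrease measures cannot be met by an unchanged subject. This stands only in part. A table shows how many responders were there at entry, but the test result still does not separate the two effects, and the ALP-decrease measures say nothing about bilirubin and albumin.

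**It is SAP detail.** An added subset analysis usually is. Here, though, the protocol itself sets the rules, the handling of missing values and the CMH strata.

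**Conclusion.** The point holds for normal bilirubin plus normal albumin, for ALP ≤1.76×ULN, and for the ALP ≤ULN summary. If ALP ≤ULN is only tabulated and not tested, the point there concerns the percentage alone. On these measures unchanged subjects count as responders, and a CMH stratified only by UDCA and bilirubin category cannot tell new response from maintenance.

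It is a modest point. It touches interpretation and sensitivity in an exploratory analysis and leaves the primary and key secondary tests alone. The loss against a baseline-non-responder test ranges from large (0.33 against 0.66) to none (0.83 against 0.66), depending on retention in the placebo arm. The albumin, retention and response rates are all assumptions. The 70% share is the most that the Version 4 synopsis permits, whereas the responder rules are quoted from Version 3.1; whether Version 4 changed them cannot be seen here.

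**What to change.** For the three affected measures:

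- **(a)** Add the responder percentage and CMH test in subjects who do not meet the rule at Baseline.
- **(b)** Report maintenance among baseline responders as a separate line for each arm. Missing values count as non-response, so show how many losses of status are due to missing data.
- **(c)** Keep the all-subject comparison, and add baseline responder status to its CMH strata.

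Do not replace the all-subject test with the restricted one, because that would discard any effect on preventing deterioration. The other three rules need no change.

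The cost is a few lines of text and some programming, since baseline classification is already to be derived. The downside is extra tables and a different denominator for each rule.
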